12.6.5.2 Hypothesis and/or parameters to be estimated

No formal statistical hypothesis testing will be performed for the secondary endpoint; however, incidence of biliary investigations and/or interventions will be reported.

12.6.5.3 Data Collection and Analysis Methods

Date of knife-to-skin contact is available on either the Transplant Operation NMP or Transplant Operation SCS CRF. The 'Action Taken' and 'If biliary investigation checked: Was there a biliary intervention' on the Adverse Event CRF as well as the Date of onset of the event are used to calculate time to event

The Kaplan-Meier rate and corresponding 95% confidence interval based on Greenwood's formula will be reported at 7-days, 30-days, 3-months, and 6-months post-transplant.

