6.8.1.3 SAFETY ASSESSMENTS

The following safety data will be collected and recorded:

- 1. Recipient infection (documented positive microbiological culture, pathological lesion, or clinical criteria met)
- 2. Biopsy-proven acute rejection episodes
- 3. Biliary investigations (MRCP, ERCP, PTC)
- 4. Biliary interventions (surgical, radiological, or endoscopic)
- 5. Hepatic vascular complications (e.g., hepatic artery stenosis, hepatic artery thrombosis, portal vein thrombosis, portal vein stenosis)
- 6. Acute Hemorrhage (requiring transfusion of two or more units of red blood cells)
- 7. Reoperation for graft related complications
- 8. Adverse event(s)

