6.8.3.3 SAFETY ASSESSMENTS

The following safety data will be collected and recorded:

- 1. Recipient infection (documented positive microbiological culture, pathological lesion, or clinical criteria met)
- 2. Biopsy-proven acute rejection episodes
- 3. Biliary investigations (MRCP, ERCP, PTC)
- 4. Biliary interventions (surgical, radiological, or endoscopic)
- 5. Hepatic vascular complications (e.g., hepatic artery stenosis, hepatic artery thrombosis, portal vein thrombosis, portal vein stenosis)
- 6. Reoperation for graft related complications
- 7. Adverse event(s)

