8.2.5 PROCEDURES FOR RECORDING ADVERSE EVENTS

It is the responsibility of the local Investigator to ensure that all adverse events (AEs, SAEs, UADEs, and device deficiencies) occurring during the course of the study are recorded. This may include but not be limited to:

- A description of the event
- The dates of the onset and resolution
- Action taken
- Outcome
- Assessment of relatedness to the device
- Assessment of relatedness to the transplant procedure
- Severity
- Whether the AE is serious or not
- Whether the AE arises from device deficiency, device malfunction, or use error

Adverse events that occur during the course of the study should be treated by established standards of care that will protect the life and health of the study subjects.

It is the responsibility of the local Investigator to collect all directly observed adverse events and all adverse events spontaneously reported by the subject. In addition, each subject should be questioned about adverse events at each visit. Adverse events should be recorded on provided adverse event data collection forms.

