12.6.5.1 Endpoint Definition

Incidence of biliary investigations and/or interventions between 7 days and 6 months post-transplant.

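### SAP 12.6.5.3 dates the biliary endpoint by adverse event onset, although the endpoint is a procedure done between 7 days and 6 months, so events can cross those limits

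*SAP*

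**What the plan says.** The protocol's table of objectives (3.2) and SAP 12.6.5.1 define the endpoint in the same words: "Incidence of biliary investigations and/or interventions between 7 days and 6 months post-transplant". The counted event is the procedure, and the window applies to it.

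SAP 12.6.5.3 gives the derivation. For the start of the clock it says: "Date of knife-to-skin contact is available on either the Transplant Operation NMP or Transplant Operation SCS CRF". For the event it names the action-taken field and the biliary-intervention question on the Adverse Event CRF, and these "as well as the Date of onset of the event are used to calculate time to event". Kaplan-Meier rates with Greenwood intervals "will be reported at 7-days, 30-days, 3-months, and 6-months post-transplant". The section does not say how the 7-day lower limit enters that analysis.

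SAP 12.6.5.2 makes the endpoint descriptive: "No formal statistical hypothesis testing will be performed for the secondary endpoint; however, incidence of biliary investigations and/or interventions will be reported".

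**The concern.** The definition counts procedures; the derivation dates complications. A procedure done for an adverse event normally comes on or after its onset, so where the two dates differ, the onset date is the earlier one.

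Three invented cases show what follows from the SAP rule taken literally:

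- **Onset day 4, procedure day 9.** The procedure is inside the window; the SAP dates the event before it.
- **Onset day 26, procedure day 36.** The SAP counts the event in the 30-day rate, although no procedure had been done by day 30.
- **Onset day 178, procedure day 190.** No procedure was done by 6 months; the SAP counts one.

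At stake is whether the reported figures describe procedure incidence, as the endpoint's name says, or the timing of complications that led to a procedure at some point.

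**Working it through.** **1. Does another passage supply the procedure date?**

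- Protocol 8.2.5 lists, for each adverse event, "The dates of the onset and resolution". It lists the action taken without a date. The list is expressly not exhaustive.
- Protocol 6.8.1.3, 6.8.2.3, 6.8.3.3 and 6.8.4.3 list biliary investigations and biliary interventions as items separate from adverse events, so the protocol treats the procedure as its own datum. They state no date field.
- SAP 12.6.1.3 does it differently for primary non-function and graft failure: it names the date of the defining event itself.
- Protocol section 9 lets the SAP govern in any disparity, so a programmer would follow 12.6.5.3.

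No passage repairs the mismatch.

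**2. Direction.** Let O be onset time and P procedure time, with O ≤ P. Every subject with P ≤ t also has O ≤ t, so at landmark t

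onset-dated rate − procedure-dated rate = Pr(O ≤ t < P) ≥ 0.

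The gap is zero at any landmark that no subject straddles, and zero everywhere if onset is recorded as the day of the procedure.

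For the incidence inside the window the error has two parts. Subjects with O ≤ 7 < P are lost if the 7-day limit is applied to onset. Subjects with O before month 6 and P after it are added.

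**3. Size.** The plan states no biliary rate, delay or power, so there is no figure to reproduce for this endpoint. Its only sample size is for EAD: [1.960·√(2·0.175·0.825) + 1.282·√(0.25·0.75 + 0.10·0.90)]² / 0.15² = 132.8, so 133 per arm and 266 in total, as stated. It is used here only to turn percentages into subjects.

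Everything else is assumed: 25% of subjects ever have an event; onset is a mixture of exponentials with means 20 days (early) and 120 days (late); delay is exponential; there is no censoring. Simulating 2,000,000 subjects gives the following percentages of subjects, onset-dated vs procedure-dated:

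| Early share | Mean delay | Day 7 | Day 30 | Month 3 | Month 6 | Inside window |
|---|---|---|---|---|---|---|
| 30% | 0 d | 3.21 / 3.21 | 9.70 / 9.70 | 16.72 / 16.72 | 21.19 / 21.19 | 17.98 / 17.98 |
| 30% | 3 d | 3.21 / 2.03 | 9.70 / 9.05 | 16.72 / 16.49 | 21.19 / 21.09 | 17.98 / 19.06 |
| 30% | 14 d | 3.21 / 0.71 | 9.70 / 6.31 | 16.72 / 15.48 | 21.19 / 20.68 | 17.98 / 19.97 |
| 60% | 3 d | 4.99 / 3.17 | 13.87 / 13.08 | 20.15 / 20.01 | 22.82 / 22.77 | 17.84 / 19.60 |
| 60% | 14 d | 4.99 / 1.12 | 13.87 / 9.29 | 20.15 / 19.22 | 22.82 / 22.53 | 17.84 / 21.42 |

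Over delays of 3 to 14 days the gaps, in percentage points, are:

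- day 7: 1.18 to 3.87
- day 30: 0.65 to 4.58
- month 3: 0.14 to 1.24
- month 6: 0.05 to 0.51

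With a 30-day mean delay and a 30% early share, the month-6 gap reaches 21.19 − 19.89 = 1.30.

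The window column applies the 7-day limit to whichever date is used. For a 30% early share and a 3-day delay it balances as 19.06 − 1.18 lost + 0.10 added = 17.98. The loss of 1.18 to 3.87 points is 1.6 to 5.1 subjects of 133 per arm. The addition, at most 0.50 points, is under one subject.

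**4. A second assumed model.** Take one exponential onset with mean a and delay with mean d. The procedure-dated share of eventual cases by t is 1 − [a·e^(−t/a) − d·e^(−t/d)]/(a − d). For a = 45, d = 5, t = 7 this is 1 − (45·0.8559 − 5·0.2466)/40 = 6.8%, against 1 − 0.8559 = 14.4% by onset. For a = 75 it is 4.2% against 8.9%. By 182 days the shares are 98.0% against 98.2% (a = 45) and 90.5% against 91.2% (a = 75).

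These are shares of eventual cases. With 25% affected, the largest of these day-7 gaps is 0.25·(14.4 − 6.8) = 1.9 points of all subjects, or about 2.5 of 133. The pattern is the same: largest early, small by month 6.

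**The case against.** The objective is to compare evidence of biliary complications, and onset is a defensible clock for a complication. Inpatients are assessed daily (Protocol 6.8.1), so long delays around day 7 are not established. The CRFs are not among the documents, and a procedure date may exist on one of them. The endpoint carries no test and both arms follow the same rule.

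All of this limits the weight of the point without removing it. If onset is the intended clock, the definition needs changing, because as written the two disagree. If a procedure date exists, the SAP does not say that it is used.

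A reader might infer three stronger things that the documents do not support:

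- **That every landmark rate is shifted.** A rate moves only if some subject straddles that landmark, and no delay is documented.
- **That early events both leave the window and inflate the 7-day rate.** These need opposite readings. The first excludes events dated before day 7; the second counts them. SAP 12.6.5.3 does not say which applies. If nothing is excluded, the day-4/day-9 case still appears in the 30-day, 3-month and 6-month rates.
- **That the rule biases the comparison of arms.** Care is open-label and local, so delay could differ by arm, but nothing shows that it does. The argument also cuts both ways: with equal onset and unequal delay, onset-dated curves agree and procedure-dated curves separate.

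**Conclusion.** The point holds as a mismatch between definition and derivation. The SAP states a dating rule that can misplace the event it defines, and no other passage corrects it. It affects only subjects whose onset and procedure fall on different sides of a limit. Under the assumed rate and delays the effect is concentrated at day 7 and day 30, with a few subjects per arm misplaced, and is small at month 6 unless delays are long. The true size is unknown and could be zero. The primary analysis, sample size and success criterion are untouched. It is worth correcting because the figures would otherwise be read as procedure incidence.

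**What to change.** In SAP 12.6.5.3:

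- Date the event by the first qualifying biliary investigation or intervention, meaning the first one done on or after day 7 and by month 6, even if the subject also had an earlier procedure. Testing only the first-ever procedure against the window would score a subject with an MRCP on day 5 and an ERCP on day 40 as having no event; under the rule proposed here the event is at day 40.
- Report procedures before day 7 separately.
- State how the 7-day landmark is then to be read. With only qualifying procedures counted, it is about zero by construction.
- Keep adverse event onset as a listing or a sensitivity analysis.

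The cost is a few sentences if the procedure date was captured. If not, it is one source query per affected subject, done retrospectively, since SAP 12.10.1 says that enrollment is complete.

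### The biliary endpoint covers day 7 to 6 months, but the SAP's Kaplan-Meier analysis has no day-7 lower bound, so its 6-month figure as written is a 0-6 month rate

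*SAP*

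**What the plan says.** SAP 12.6.5.1 defines secondary endpoint #5 as "Incidence of biliary investigations and/or interventions between 7 days and 6 months post-transplant". The protocol synopsis and the endpoint table in protocol 3.2.2 give the same window.

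SAP 12.6.5.2 plans no formal test and states only that "incidence of biliary investigations and/or interventions will be reported"; the window is not repeated there.

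SAP 12.6.5.3 gives the method:

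- The starting date: "Date of knife-to-skin contact is available on either the Transplant Operation NMP or Transplant Operation SCS CRF".
- The event date: the biliary fields on the Adverse Event CRF "as well as the Date of onset of the event are used to calculate time to event".
- The estimate: "The Kaplan-Meier rate and corresponding 95% confidence interval based on Greenwood's formula", which "will be reported at 7-days, 30-days, 3-months, and 6-months post-transplant".

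Nothing in 12.6.5.3 removes onsets before day 7, starts the risk set at day 7, or says what happens to a recipient with both a first-week and a later event. Protocol 6.8.1.3 collects biliary investigations and interventions during the inpatient stay, so first-week events can be in the data.

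**The concern.** The method does not estimate the endpoint it sits under. A time-to-first-event curve from the operation counts everything from day 0, so its 6-month value mixes first-week events with the later events that the endpoint isolates. If first-week rates differ between the NMP and SCS arms, part of that difference would appear in a figure labelled as a day-7-to-6-month result. The trial is open-label and recipient management follows local protocols, so such a difference is possible.

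There is a second, smaller dating problem. Onset date stands in for procedure date. An event with onset on day 3 that leads to a procedure on day 20 would be placed outside the window, although the investigation or intervention took place inside it.

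**Working it through.** The plan states no numerical figure for this endpoint, so there is nothing to reproduce. The check is the two possible readings, then the size under stated assumptions.

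**Two readings**

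1. *12.6.5.3 followed as written.* Time runs from knife-to-skin to onset and all onsets count. The 7-day rate is informative, and the 6-month rate covers 0-6 months. This does not match 12.6.5.1.
2. *12.6.5.1 taken to filter the events.* Only onsets from day 7 count. The 6-month rate can be right, but the 7-day rate is zero by construction, apart from events dated exactly day 7.

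Protocol section 9 lets the SAP prevail over the protocol, but this conflict is inside the SAP.

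**Size under the first reading**

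Let e be the first-week event rate, L1 the day-7-to-6-month risk without a first-week event, and L2 that risk after one. All three are assumed.

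- From-transplant Kaplan-Meier at 6 months: e + (1 - e)L1
- Incidence as defined in 12.6.5.1: (1 - e)L1 + e·L2
- Excess: e(1 - L2)

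| e | Excess in points, L2 from 50% down to 10% |
|---|---|
| 0% | 0 |
| 1% | 0.5-0.9 |
| 2% | 1.0-1.8 |
| 5% | 2.5-4.5 |
| 10% | 5.0-9.0 |

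*Worked case:* e = 5%, L1 = 15%, L2 = 50%. From transplant: 0.05 + 0.95 × 0.15 = 19.25%. Defined: 0.95 × 0.15 + 0.05 × 0.50 = 16.75%. Excess: 2.5 points.

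**Effect on the arm comparison**

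With equal defined incidence and equal L2 in both arms, the apparent difference is (eA - eB)(1 - L2), or 0.5-0.9 points per 1-point difference in first-week rate. For example, take 15% risk after day 7 in both arms whether or not there was an early event, and first-week rates of 1% and 5%. The 0-6 month rates are 1 - 0.99 × 0.85 = 15.85% and 1 - 0.95 × 0.85 = 19.25%. The gap of 3.4 points comes only from the first week.

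**Scale against sampling error**

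For two arms of 133 (half of the planned 266) at an assumed 15%, the 95% half-width of the difference is 1.96 × √(2 × 0.15 × 0.85 / 133) = 8.6 points. It is also 8.6 points for arms of 120 and 146.

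**Check with dropout**

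A simulation of 2 million recipients gave 10% of them a dropout time uniform over 0-182 days, with L1 = 15%.

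| Quantity | e = 5%, L2 = 50% | e = 10%, L2 = 50% |
|---|---|---|
| Defined incidence | 16.75% | 18.5% |
| Curve from transplant | 19.3% | 23.5% |
| Curve started at day 7, first in-window event | 16.8% | 18.5% |
| 1 - S(6 months)/S(7 days) | 15.1% | 15.0% |
| Simple proportion ignoring censoring | 16.0% | 17.5% |

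At e = 0 the from-transplant and day-7-start curves both give 15.0%. Of the estimators compared, only the curve restarted at day 7 recovers the defined incidence when first-week events occur.

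**The case against.** The best defence has four parts.

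*The definition governs its subsections.* On this view 12.6.5.3 need not repeat the window, and the fault is an ambiguity with one uninformative time point. The reading is available, but the methods text does not state it, and it makes a requested estimate meaningless. Either way 12.6.5.3 needs correcting.

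*The 7-day rate is reported, so a reader can subtract it.* First-week events would indeed be visible by arm, which limits the harm. Subtraction gives (1 - e)L1, however, and omits in-window events in recipients who already had a first-week event. In the worked case that is 14.25% against a defined 16.75%. The SAP plans no such subtraction and gives no interval for it.

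*The size depends on how the window is read.* This stands in part. If recipients with a first-week event were not counted again, the excess would be the whole first-week rate: 5.0 points at e = 5%, against 2.5-4.5 above. The literal definition does not exclude those recipients, so e(1 - L2) is used here.

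*A day-7 risk set departs from the all-transplanted population in SAP 12.6.* It does not. A recipient censored before day 7 contributes no in-window event, so the day-7-start curve equals a curve over all transplanted recipients that counts only in-window events.

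It also stands that the endpoint is untested, and that reaching the 8.6-point half-width would take a first-week arm difference of about 10-17 points (8.6/0.9 to 8.6/0.5). Nothing in the documents suggests one.

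**Conclusion.** The concern holds. As written, SAP 12.6.5.3 yields a 0-6 month rate for an endpoint defined from day 7 to 6 months, and the only reading that avoids this empties the 7-day estimate. The overstatement is e(1 - L2): 0.5-0.9 points at a first-week rate of 1% and 2.5-4.5 at 5%, with L2 assumed at 10-50%, and none if there are no first-week events. These rates are assumptions, since the documents give no biliary rates.

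A plausible shift lies within sampling error, and the primary test, alpha and power are untouched. The fault is that the reported figure does not measure the stated endpoint. It should be corrected. The onset-date point is a secondary limitation whose size cannot be judged from the documents.

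**What to change.** Amend SAP 12.6.5.3 as follows:

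- Estimate the endpoint by arm with a Kaplan-Meier curve that starts at day 7, among recipients still at risk then. Define day 7 as elapsed time from knife-to-skin, because the SAP counts days differently elsewhere: 12.1 calls the attempted-transplant date day 1, 12.6.1.3 uses knife-to-skin as day 0, and 11.3 times visits from the end of the procedure.
- Count the first biliary investigation or intervention from day 7 to 6 months, whatever happened earlier.
- Keep the Greenwood intervals at 30 days, 3 months and 6 months, and state by arm how many recipients were no longer at risk at day 7 and why.
- Report first-week events separately, and label any curve from transplant as a 0-6 month rate.
- Date events by the procedure where that date is recorded; otherwise use onset and state the limitation.

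The cost is SAP wording and a small programming change. Knife-to-skin and onset dates are already collected. Whether a procedure date exists is not shown: protocol 8.2.5 lists "The dates of the onset and resolution", but that list is not exhaustive. SAP version 4.0 already corrected the descriptions of secondary endpoints #6 and #7, so there is a precedent for an amendment of this kind.

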12.6.6 Secondary Objective #6

To assess the feasibility and safety of NMP as a method of organ storage and transportation.

12.6.6.1 Endpoint Definition

Incidence of one or more of the following per randomized liver: (i) EAD; (ii) discard (non-transplant) of a retrieved liver; (iii) primary non-function.

12.6.6.2 Hypothesis and/or parameters to be estimated

No formal statistical hypothesis testing will be performed for this secondary endpoint; however, the following composite measure will be reported: incidence of one or more of the following per randomized liver: (i) EAD; (ii) discard (non-transplant) of a retrieved liver; (iii) primary non-function.

12.6.6.3 Data Collection and Analysis Methods

The Inpatient Stay (Day 1 through Day 10 Follow-up) CRF contains all variables to report on EAD as well as primary non-function. The Study Withdrawal Form CRF contains all variables pertaining to the discard (non-transplant) of a retrieved liver.

The incidence of either EAD, discard of a retrieved liver, or primary non-function will be measured.

12.6.7 Secondary Objective #7

To compare organ utilization between NMP and SCS.

12.6.7.1 Endpoint Definition

Incidence of livers randomized but not transplanted and reasons for not-transplanting.

12.6.7.2 Hypothesis and/or parameters to be estimated

No formal statistical hypothesis testing will be performed for the secondary endpoint, however, incidence of livers randomized but not transplanted will be reported for both NMP and SCS.

12.6.7.3 Data Collection and Analysis Methods

All relevant information to this endpoint can be found on the Study Withdrawal Form CRF (Questions: 'Reason for Study Withdrawal', 'If liver not suitable for retrieval', 'If liver discarded before transportation', 'If liver discarded following transportation', and 'If subject was not eligible to proceed with transplant').

The incidence of livers randomized but not transplanted will be reported.

12.6.8 Secondary Objective #8

To assess the health economic implications of normothermic liver perfusion.

12.6.8.1 Endpoint Definition

Logistical and healthcare costs (length of stay in ICU and hospital) and quality of life measures.

12.6.8.2 Hypothesis and/or parameters to be estimated

No formal statistical hypothesis testing will be performed for the secondary endpoint, however, the following will be reported: length of stay in high level care (ICU) post-transplant, total length of hospital stay post-transplant, and mobility, self-care, usual activities, pain/discomfort, anxiety/depression, and VAS score (all part of the EQ-5D).

12.6.8.3 Data Collection and Analysis Methods

Length of stay in high level care (ICU) post-transplant as well as total length of hospital stay post-transplant are reported on the Discharge Form CRF. The Mobility, Self-Care, Usual Activities, Pain/Discomfort, Anxiety/Depression, and VAS Score are all reported on the EQ-5D CRF.

Length of hospital stay (total and in ICU) will be summarized continuously. The EQ-5D measures will be summarized at each available time point. Mobility, self-care, usual activities, pain/discomfort, and anxiety/depression are all categorical variables and will be reported as such. VAS Score is continuous and will be summarized appropriately.

12.7 Exploratory Analyses

A logistic regression model will be used to examine the possible explanatory effects of baseline subject characteristics (in the presence of the treatment indicator variable), namely: race, age, gender, and number of liver transplants received (primary or secondary).

Secondary analysis may be stratified by recipient center and donor type (DBD or DCD) for exploratory purposes.

Ver 4.0 09SEP2020

Additional exploratory analyses will include those that assess a learning curve or enhanced training effect.

